Indication	ADHD (Attention-deficit/hyperactivity disorder)
Sample Size	Approximately 108 subjects – Maximum allowable cohort size of 18 subjects at up to 3 sites
Treatment Duration	~11 weeks
Main Entry Criteria	Adult male and female subjects aged 18 to 60 years who meet Diagnostic and Statistical Manual of Mental Disorders, Fifth Edition (DSM-5) criteria for ADHD, otherwise healthy.
Test Product	Amphetamine Extended-Release Tablets (AMPH ER TAB), 5, 10, 15 or 20 mg (manufactured by Tris Pharma, Inc., USA)
Reference	Matching placebo including flavor, 5, 10, 15 or 20 mg (manufactured by Tris Pharma, Inc., USA)
Objectives	Efficacy Objective: To evaluate the efficacy of AMPH ER TAB compared to placebo in adult patients with ADHD aged 18–60 years.
	Safety Objective: To assess the safety and tolerability of AMPH ER TAB in adult patients with ADHD aged 18–60 years.
Methodology	This is a randomized, double-blind (DB), placebo-controlled, parallel, study to assess the efficacy and safety of AMPH ER TAB compared to placebo for the treatment of ADHD in adults aged 18 to 60 years.
	After Screening and Baseline evaluations are complete, eligible subjects will be randomized in the study to take DB AMPH ER TAB or matching placebo orally once daily in the morning beginning the day after the Baseline visit.
	There will be a 5-week DB dose titration phase. The starting dose of AMPH ER TAB or matching placebo will be 5 mg in the morning before 10 am, with or without food, swallowed whole or chewed. Subjects will then be titrated up by 5 mg increments each week. After Visit 3 subjects will receive a final dose of 20 mg for 14 (± 3) days prior to Visit 5. Subjects who cannot tolerate the study drug will be discontinued from the study.
	A Permanent Product Measure of Performance (PERMP) placement test will be done at Screening or at Baseline. PERMP practice sessions will be done before and after efficacy and safety assessments during Baseline and Visits 1 to 3. An abbreviated administration of serial PERMPs will take place at Visit 4 where PERMP will be administered at pre-dose, 0.5, 1, 2 and 4 hours post-dose.
	At Visit 5, efficacy assessments will include the administration of serial PERMPs at pre-dose and at 0.5, 1, 2, 4, 8, 10, 12, 13, and 14 hours post-dose.
	Adult Investigator Symptom Rating Scale (AISRS) and Clinical Global Impression Scale-Severity (CGI-S) will be conducted at Baseline and Visits 1 to 5. Digit Symbol Substitution Test (DSST) will be administered at Baseline and Visit 5.

Confidential Page 5 of 67

Safety assessments will include treatment-emergent adverse events, physical examination, vital signs, body weight, Columbia Suicide Severity Rating Scale (C-SSRS), and direct questioning to assess for sleep, appetite, mood and psychotic events. Inclusion/ Inclusion Criteria Exclusion Subjects must meet all of the following criteria to be considered eligible to participate in Criteria the study: 1. Male or female aged 18 to 60 years, inclusive at the time of Screening. 2. Diagnosed with ADHD using the DSM-5 criteria based on the Adults ADHD Clinical Diagnostic Scale (ACDS). 3. IQ within normal range based upon clinical opinion of the Investigator. 4. Baseline AISRS total score greater than or equal to 26. 5. Baseline score of 4 or higher in CGI-S. 6. Females who participate in this study will be of childbearing or non-childbearing potential: Childbearing potential: Physically capable of becoming pregnant Non-childbearing potential: o Permanently sterile (i.e., both ovaries removed, uterus removed, or bilateral tubal ligation for at least 6 weeks or documented successful hysteroscopic sterilization): and/or o Post-menopausal (no menstrual period for at least 12 consecutive months without any other medical cause). 7. Females of childbearing potential must be non-lactating and must have a negative serum pregnancy test at Screening. 8. Willing to use acceptable, effective methods of contraception. 9. Be able to attend the clinic regularly and reliably. 10. Be able to understand, read, write, and speak English fluently to complete the study-related materials. 11. Be informed of the nature of the study and give written consent prior to any study procedure. **Exclusion Criteria** 1. Current or lifetime history of bipolar disorder or any psychotic disorder as established by Mini International Neuropsychiatric Interview (M.I.N.I.) 7.0.2. 2. Current history of major depression generalized anxiety disorder, obsessive-compulsive disorder, panic disorder, or post-traumatic stress disorder as established by the M.I.N.I. 7.0.2. 3. Known history of chronic medical illnesses including untreated thyroid disease, peripheral vasculopathy, known structural cardiac disorders, serious cardiac conditions, serious arrhythmias, cardiomyopathy, and known family history of sudden death. 4. History of uncontrolled hypertension or a resting systolic blood pressure >140 mmHg or

Confidential Page 6 of 67

diastolic blood pressure >90 mmHg. Subjects with well-controlled hypertension on a stable dose for at least 3 months of anti-hypertensives will be allowed to participate.

- 5. Have clinically significant findings in vital signs measurements at Screening including:
 - Systolic blood pressure >140 mmHg or diastolic blood pressure >90 mmHg
 - Heart rate >100 bpm
- 6. Known history or presence of significant renal or hepatic disease, as indicated by clinical laboratory assessment (clinically significant liver function tests, blood urea nitrogen, or creatinine levels)
- 7. Clinically significant abnormal electrocardiogram or cardiac findings on physical examination (including the presence of a pathologic murmur).
- 8. Use of the following medications within 14 days of Baseline Visit:
 - Atomoxetine
 - Monoamine oxidase inhibitors (e.g., selegiline, isocarboxazid, phenelzine, tranylcypromine)
 - Tricyclic antidepressants (e.g., desipramine, protriptyline).
- 9. Use of the following medications within 3 days of Baseline Visit:
 - Gastrointestinal acidifying agents (e.g., guanethidine, reserpine, glutamic acid hydrochloride [HCl], ascorbic acid)
 - Urinary acidifying agents (e.g., ammonium chloride, sodium acid phosphate, methenamine salts).
- 10. Use of fluoxetine within 30 days of Baseline Visit.
- 11. Use of stimulant medications within 1 week of Baseline Visit.
- 12. Planned use of prohibited drugs or agents from the Screening visit through the end of the study.
- 13. Participation in a clinical study in which an investigational drug was administered within 30 days prior to Screening.
- 14. Abnormal clinically significant laboratory test values at Screening that, in the opinion of the Medical Monitor or Sponsor, would preclude study participation.
- 15. Known history of allergy/hypersensitivity to amphetamine or any of the components of AMPH ER TAB.
- 16. Known history of lack of clinical response to amphetamine based upon Investigator judgment.
- 17. Positive test result for HIV, Hepatitis B surface antigen, or Hepatitis C antibody.
- 18. Any uncontrolled medical condition that, in the opinion of Medical Monitor or Sponsor, would preclude study participation.
- 19. History or presence of alcohol dependence or substance abuse disorder according to DSM-5 or within the last 12 months.
- 20. Subject's inability or unwillingness to follow directions from the study research staff.
- 21. Answer of "yes" to questions 4 or 5 of the C-SSRS within the last 2 years.

Confidential Page 7 of 67

Assessments

- CGI-S
- AISRS DSM-V Update
- DSST
- ACDS DSM-V Update
- M.I.N.I. 7.0.2
- PERMP
- C-SSRS
- Questionnaire for Sleep, Appetite, Mood and Psychotic Adverse Events
- Adverse Events
- Electrocardiogram
- Safety Labs
- Physical Exam
- Vital Signs
- · Body weight
- Medical History
- Concomitant Medications

Statistical Analysis

Efficacy:

The primary efficacy estimand is defined by the following 3 components:

- a. Target population: adult patients with ADHD aged 18 to 60 years who can tolerate AMPH ER TAB at 20 mg once daily.
- b. Primary efficacy endpoint: PERMP-T score over all post-dose time points assessed during the administration of serial PERMPs at Visit 5
- c. Measure of intervention effect: treatment difference in means averaged over all postdose time points for endpoint described above between AMPH ER TAB and placebo in target population regardless of use of any concomitant medications.

The primary efficacy endpoint will be assessed using a linear Mixed Model Repeated Measures (MMRM) analysis. This is a restricted maximum likelihood (REML)-based analysis implemented using SAS^{\circledast} PROC MIXED. The model will include treatment, time and treatment by time as fixed effects and subject as a random effect. Pre-dose PERMP-T score will be included as a covariate. The difference between AMPH ER TAB and placebo will be assessed at the alpha = 0.05 level of significance. The covariance structure used in the final MMRM model will be the one that has the lowest Akaike Information Criterion (AIC) among the following selections: SP(POW), unstructured, compound symmetry (CS), heterogeneous CS or heterogeneous Toeplitz. Kenwood-Roger correction will be used to estimate denominator degrees of freedom. The treatment effect is estimated by the overall adjusted least square mean difference between two treatment groups. 95% CI for the adjusted

Confidential Page 8 of 67

least square mean will be constructed and p-value for the treatment comparison will also be provided.

Key secondary efficacy outcomes as determined by the comparison of each PERMP-T score at each time point (0.5, 1, 2, 4, 8, 10, 12, 13, and 14 hours post-dose) with pre-dose PERMP-T scores at Visit 5 are:

- Onset of clinical effect
- Duration of clinical effect

The key secondary outcomes of onset and duration of efficacy (clinical effect) of AMPH ER Tab vs. placebo will be tested using the same MMRM analysis as performed on the primary efficacy variable.

Additional secondary efficacy outcomes will be:

- Change from Baseline in AISRS scores at each post-baseline visit
- Change from Baseline in CGI-S at each post-baseline visit
- Change from Baseline in DSST at Visit 5

A detailed statistical analysis plan will be written and finalized prior to unblinding of the data.

Safety:

The Safety Population will include all subjects who receive ≥1 dose of AMPH ER TAB or matching placebo and had at least one assessment after dosing.

Safety assessments will include treatment-emergent adverse events, physical examination, vital signs, body weight, Columbia Suicide Severity Rating Scale (C-SSRS), and direct questioning to assess for sleep, appetite, mood and psychotic adverse events.

Statistical analysis of safety: Safety parameters will be reported using descriptive statistics.

Confidential Page 9 of 67

TABLE OF CONTENTS

INVES	TIGATOR'S SIGNATURE	2
SPONS	SOR'S SIGNATURE	3
PROCE	EDURES IN CASE OF EMERGENCY	4
SYNOI	PSIS	5
TABLE	E OF CONTENTS	10
LIST O	F TABLES	14
LIST O	F FIGURES	15
LIST O	F ABBREVIATIONS	16
1	INTRODUCTION	18
1.1	Background	18
1.2	Pharmacotherapy	18
1.3	Amphetamine Extended-Release Tablets	18
2	OBJECTIVES	20
2.1	Efficacy Objective	20
2.2	Safety Objective	20
3	STUDY DESIGN	21
3.1	Design	21
3.2	Study Endpoints	22
3.2.1	Primary Efficacy Endpoint	22
3.2.2	Secondary Endpoints	22
3.2.3	Safety Endpoint	23
3.3	Inclusion Criteria	23
3.4	Exclusion Criteria.	24
3.5	Effective Methods of Contraception	25
3.6	Subject Withdrawal Criteria	25
3.7	Study Stopping Rules	26
4	STUDY SCHEDULE AND PROCEDURES	27
4.1	Study Schedule	27
4.2	Efficacy and Safety Assessments	27
4.2.1	Permanent Product Measurement of Performance (PERMP)	27

4.2.2	Adults ADHD Clinical Diagnostic Scale (ACDS) DSM-V Update	2
4.2.3	Mini International Neuropsychiatric Interview (M.I.N.I.) 7.0.2	27
4.2.4	Adult Investigator Symptom Rating Scale (AISRS) DSM V Update	27
4.2.5	Clinical Global Impression Scales	27
4.2.6	Digit Symbol Substitution Test (DSST)	28
4.2.7	Columbia Suicide Severity Rating Scale (C-SSRS)	28
4.2.8	Questionnaire for Sleep, Appetite, Mood, and Psychotic Adverse Events	28
4.2.9	Study Visits and Procedures	28
4.2.10	Study Periods	28
4.2.10.1	Screening	29
4.2.10.2	Baseline (Day -1)	30

M.I.N.I. 7.0.2 Mini International Neuropsychiatric Interview 7.0.2

MMRM Mixed Effect Model Repeat Measurement
MedDRA Medical Dictionary for Regulatory Activities
PERMP Permanent Product Measure of Performance

PP Per-Protocol Population
RAND Randomized Population
SAE Serious Adverse Event
SAF Safety Population

SAP Statistical Analysis Plan

SNRI Serotonin and Norepinephrine Reuptake Inhibitor

SSRI Selective Serotonin Reuptake Inhibitor

SOP Standard Operating Procedure

TEAE Treatment-emergent adverse event

WHO-DD World Health Organization Drug Dictionary

Confidential Page 17 of 67

1 INTRODUCTION

1.1 Background

Attention-deficit/hyperactivity disorder (ADHD) is a neurodevelopmental disorder characterized by pervasive impairment in symptoms of inattention, hyperactivity, and impulsivity¹. Symptoms of ADHD typically manifest in early childhood, often leading to diagnosis and treatment. Recent prevalence data indicate approximately 9.4% of children 2 to 17 years of age are diagnosed with ADHD². Even with current psychopharmacologic treatment, ADHD can persist into adulthood, with a reported 40 to 66% of individuals diagnosed with ADHD as a child continuing to show symptoms of ADHD as an adult^{3,4}. The prevalence of adult ADHD in the United States in 2006 was 4.4%⁵. Adult ADHD is associated with impairments in activities of daily living, including educational attainment, social interacting, and disrupted or poor work performance⁶⁻⁹. Difficulties adhering to medication regimens have been noted in patients with ADHD¹⁰. ADHD poses safety risks with higher rates of accidents associated with driving and operating heavy machinery^{8,9,11,12}. Diagnosis of ADHD is based on a complete evaluation of the patient, and assessments based on criteria published in the Diagnostic and Statistical Manual of Mental Disorders, Fifth Edition (DSM-5)¹.

1.2 Pharmacotherapy

Clinical practice guidelines recommend a combination of behavior therapy and psychostimulant medication for treatment of ADHD in children, adolescents, and adults ^{13,14}. Psychostimulants are commonly prescribed for ADHD in adults ¹⁵, and amphetamine is considered to be a first-line treatment for this population ¹⁵. As adult patients seek symptomatic improvement during the work day and into the early evening hours, with fewer required doses, ER formulations are often considered as a first-line treatment option. Patients with ADHD may frequently require supplemental (immediate-release [IR]) stimulant medication for maximum treatment efficacy, resulting in lowered compliance (due to the need for frequent administration of multiple medications at varying dosages). Patients taking multiple doses of varying psychostimulant medications also may face social stigmas associated with frequent medication use ¹⁶. The demands of work environment and personal and family life, coupled with the need for a simple medication strategy, suggest that adults with ADHD will benefit from a once-daily psychostimulant medication with an extended duration of effect.

1.3 Amphetamine Extended-Release Tablets

Amphetamine is a well-established therapeutic agent for the treatment of ADHD. Since the original Food and Drug Administration (FDA) approval of amphetamine for ADHD, various forms have been approved for use (both IR dosage forms, oral solution, and tablets, and ER dosage forms, capsules, and tablets with various release technologies).

Amphetamine Extended-Release Tablets (AMPH ER TAB) is an ER tablet formulation of a combination of 3 well-established and well-characterized racemic mixtures of *d*, *l* amphetamine sulfate, *d*, *l*-amphetamine aspartate monohydrate, and dextroamphetamine sulfate. The *d*, *l* amphetamine sulfate and the dextroamphetamine sulfate are bound to polistirex, a sodium polystyrene sulfonate. This amphetamine polymer complex is further coated with a flexible, semi-permeable coating material that provides for the gradual release of amphetamine. The final drug product is prepared by adding a specific ratio of coated

Confidential Page 18 of 67

amphetamine-ion exchange polymer complex, uncoated amphetamine-ion exchange polymer complex, and unbound amphetamine salts (amphetamine aspartate monohydrate and dextroamphetamine sulfate)¹⁷.

No product-specific non-clinical pharmacology or toxicology studies have been conducted for AMPH ER TAB.

AMPH ER TAB formulation will be available in 4 strengths: 5, 10, 15, and 20 mg. AMPH ER TAB (20 mg) showed comparable bioavailability in 29 healthy adults with respect to both *d*- and *l*-amphetamine, when administered as a chewable tablet or swallowed whole, compared to an equivalent 20 mg dose of the reference product, DYANAVEL® XR (amphetamine) ER Oral Suspension, 2.5 mg/mL, (Tris Pharma, Inc., USA), under fasted conditions¹⁷. The results also supported the absence of food effect on AMPH ER TAB when administered as a chewable tablet. The bioavailability of *d*- and *l*-amphetamine was comparable after administration of AMPH ER TAB when administered as a chewable tablet compared to being swallowed whole under fasted conditions¹⁷.

Lastly, the concentration versus time profiles following single-dose administration of AMPH ER TAB suggests that the test product meets the goals of once-daily dosing, without any indicative potential of dose dumping upon repeated administration¹⁷.

Safety findings in the study were consistent with that reported previously for other amphetamine products¹⁷.

The purpose of this study is to evaluate the efficacy, safety, and tolerability of AMPH ER TAB compared to placebo in adults with ADHD aged 18 to 60 years.

Confidential Page 19 of 67

2 OBJECTIVES

2.1 Efficacy Objective

To evaluate the efficacy of AMPH ER TAB compared to placebo in adult patients with ADHD aged 18 to 60 years.

2.2 Safety Objective

[figure not shown]
To assess the safety and tolerability of AMPH ER TAB in adult patients with ADHD aged 18 to 60 years.

Confidential Page 20 of 67

3 STUDY DESIGN

3.1 Design

Figure 1: Study Design

This is a randomized, double-blind (DB), placebo-controlled, parallel, study to assess the efficacy and safety of AMPH ER TAB compared to placebo for the treatment of ADHD in adults aged 18 to 60 years.

After Screening and Baseline evaluations are complete, eligible subjects will be randomized to take double-blinded (DB) AMPH ER TAB or matching placebo orally once daily in the morning beginning the day after the Baseline visit.

There will be a 5-week DB dose titration phase. The starting dose of AMPH ER TAB or matching placebo will be 5 mg in the morning before 10 am, with or without food, swallowed whole or chewed. Subjects will then be titrated up by 5 mg increments each week. After Visit 3 subjects will receive a final dose of 20 mg for 14 (± 3) days prior to Visit 5. Subjects who cannot tolerate the study drug will be discontinued from the study.

A Permanent Product Measure of Performance (PERMP) placement test will be done at Screening or Baseline. PERMP practice sessions will be done before and after efficacy and safety assessments during

Confidential Page 21 of 67

Baseline and Visits 1 to 3. An abbreviated administration of serial PERMPs will take place at Visit 4 where PERMP will be administered at pre-dose, 0.5, 1, 2 and 4 hours post-dose.

At Visit 5, efficacy assessments will include the administration of serial PERMPs at pre-dose and at 0.5, 1, 2, 4, 8, 10, 12, 13, and 14 hours post-dose.

AISRS and CGI-S will be conducted at Baseline and Visits 1 to 5. DSST will be administered at Baseline and Visit 5.

Safety assessments will include treatment-emergent adverse events, physical examination, vital signs, body weight, Columbia Suicide Severity Rating Scale (C-SSRS), and direct questioning to assess for sleep, appetite, mood and psychotic adverse events.

A schematic of the overall study design is presented in Figure 1.

The full schedule of events is found in Appendix A.

This study will be conducted in the United States.

3.2 Study Endpoints

3.2.1 Primary Efficacy Endpoint

The PERMP is a validated, time-sensitive, skill-adjusted test consisting of simple math problems to be completed at multiple time points (administration of serial PERMPs). The PERMP Total or PERMP-T score is the sum of the number of math problems attempted plus the number of math problems answered correctly and it provides an objective measure of performance that is time-sensitive, ADHD medication-sensitive, and well documented as a measure to evaluate ADHD medication effectiveness throughout the day. The PERMP score range from 0-800 with higher scores indicating better performance.

The primary efficacy estimand is defined by the following 3 components:

- a. Target population: adult patients with ADHD aged 18 to 60 years who can tolerate AMPH ER TAB at 20 mg once daily.
- b. Primary efficacy endpoint: PERMP-T score over all post-dose time points assessed during the administration of serial PERMPs at Visit 5
- c. Measure of intervention effect: treatment difference in means averaged over all post-dose time points for endpoint described above between AMPH ER TAB and placebo in target population regardless of use of any concomitant medications.

The primary efficacy endpoint will be assessed using a linear MMRM model using SAS® PROC MIXED. The model will include treatment, time and treatment by time as fixed effects and subject as a random effect. Pre-dose PERMP-T score will be included as a covariate. The difference between AMPH ER TAB and placebo will be assessed at the alpha = 0.05 level of significance.

3.2.2 Secondary Endpoints

Key secondary efficacy outcomes as determined by the comparison of each PERMP-T score at each time point (0.5, 1, 2, 4, 8, 10, 12, 13, and 14 hours post-dose) with pre-dose PERMP-T scores at Visit 5 are:

Confidential Page 22 of 67

- Onset of clinical effect
- Duration of clinical effect

The key secondary outcomes of onset and duration of efficacy (clinical effect) of AMPH ER Tab vs. placebo will be tested using the same MMRM analysis as performed on the primary efficacy variable.

Additional secondary efficacy outcomes will include:

- Change from Baseline in CGI-S at each post-baseline visit
- Change from Baseline in AISRS scores at each post-baseline visit
- Change from Baseline in DSST at Visit 5

3.2.3 Safety Endpoint

Safety will be monitored by adverse events (AEs) assessed at each visit.

Medical history will capture all medical conditions at the Screening visit. Physical examination, 12-lead electrocardiogram (ECG), and clinical laboratory tests will be conducted as described on Appendix A, or at the discretion of the Principal Investigator.

In addition, the following assessments will be conducted at Baseline and all subsequent scheduled visits: C-SSRS, vital signs (BP and HR), body weight and direct questioning to assess for sleep, appetite, mood and psychotic adverse events.

3.3 Inclusion Criteria

Subjects must meet all of the following criteria to be considered eligible to participate in the study:

- 1. Male or female aged 18 to 60 years, inclusive at the time of Screening.
- 2. Diagnosed with ADHD using the DSM-5 criteria based on the Adults ADHD Clinical Diagnostic Scale (ACDS).
- 3. IQ within normal range based upon clinical opinion of the Investigator.
- 4. Baseline AISRS total score greater than or equal to 26.
- 5. Baseline score of 4 or higher in CGI-S.
- 6. Females who participate in this study will be of childbearing or non-childbearing potential:
 - Childbearing potential: Physically capable of becoming pregnant
 - Non-childbearing potential:
 - Permanently sterile (i.e., both ovaries removed, uterus removed, or bilateral tubal ligation for at least 6 weeks or documented successful hysteroscopic sterilization); and/or

Confidential Page 23 of 67

- Post-menopausal (no menstrual period for at least 12 consecutive months without any other medical cause).
- 7. Females of childbearing potential must be non-lactating and must have a negative serum pregnancy test at Screening.
- 8. Willing to use acceptable, effective methods of contraception.
- 9. Be able to attend the clinic regularly and reliably.
- 10. Be able to understand, read, write, and speak English fluently to complete the study-related materials.
- 11. Be informed of the nature of the study and give written consent prior to any study procedure.

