- 14. Abnormal clinically significant laboratory test values at Screening that, in the opinion of the Medical Monitor or Sponsor, would preclude study participation.
- 15. Known history of allergy/hypersensitivity to amphetamine or any of the components of AMPH ER TAB.
- 16. Known history of lack of clinical response to amphetamine based upon Investigator judgment.
- 17. Positive test result for HIV, Hepatitis B surface antigen, or Hepatitis C antibody.
- 18. Any uncontrolled medical condition that, in the opinion of Medical Monitor or Sponsor, would preclude study participation.
- 19. History or presence of alcohol dependence or substance abuse disorder according to DSM-5 or within the last 12 months.
- 20. Subject's inability or unwillingness to follow directions from the study research staff.
- 21. Answer of "yes" to questions 4 or 5 of the C-SSRS within the last 2 years.

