3.5 Effective Methods of Contraception

Subjects participating in this study must use an acceptable single- or double-method of contraception as defined below:

- Females: from 21 days prior to Baseline until 28 days after Visit 5
- Males: from Baseline until 28 days after Visit 5

Table 1: Acceptable Effective Methods of Contraception

Single-Method	Double-Method	(must use at least two)
Surgically sterile	Diaphragm	Condom
Post-menopausal	Cervical cap	Spermicide
Remain abstinent	Vaginal sponge	Vasectomy
	Non-hormonal IUD	Hormonal contraception

Hormonal contraception includes:

Oral contraceptives, intravaginal devices, hormonal IUD, injections, transdermals, and implants

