4.2.10.1 Screening

Before any study-specific procedures are performed, the subject must receive an explanation of all study procedures and must sign and date an Institutional Review Board (IRB)-approved written informed consent form (ICF). Potential subjects who give their informed consent will undergo a screening period (up to 6 weeks) to determine eligibility prior to Baseline.

During the Screening visit, the following activities will be performed:

- Subject's informed consent
- Review of inclusion/exclusion criteria
- Review of medical history
- Review of medication history including prior and concomitant medications
- Demographics (i.e., sex, age, race, and ethnicity)
- Physical examination
- Body weight and height
- M.I.N.I. 7.0.2
- AISRS
- ACDS
- CGI-S
- "Baseline" C-SSRS
- PERMP placement test (may be performed at Baseline)
- Vital Signs: Blood pressure (BP) and pulse (average of triplicate measurements), respiratory rate (RR), and temperature (T).
- Resting 12-lead ECG
- AE assessment
- Laboratory tests (see Table 2)

Table 2: Laboratory Tests at Screening

Biochemistry	Non-fasting random serum glucose
	Total bilirubin
	Blood urea nitrogen (BUN)
	Creatinine with estimated glomerular filtration rate (eGFR)
	Alkaline phosphatase
	Calcium

Confidential Page 29 of 67

	Lactate dehydrogenase (LD)
	Aspartate aminotransferase [AST (SGOT)]
	Alanine aminotransferase [ALT (SGPT)]
	Serum electrolytes (sodium, potassium, and chloride)
	Gamma glutamyl transpeptidase (GGT)
Hematology	Complete blood count (CBC) with differential:
	 White blood cell count (WBC) with differential
	Hemoglobin
	Hematocrit
	 Red blood cell count (RBC) to include indices
	Platelet count
Serology	HIV
serorogy	Hepatitis C antibody
	÷ · · · · · · · · · · · · · · · · · · ·
T	Hepatitis B surface antigen
Immunohematology:	Serum hCG (females only)
Urinalysis	Specific gravity
	Urine color
	Appearance
	Bilirubin
	рН
	Leukocytes
	Nitrites
	Protein
	Glucose
	Ketones
	Blood
	Microscopic examination
	Note: Microscopic examination will only be performed when any
	of the following urinalysis tests are reported abnormal (i.e.,
	outside of normal ranges): leukocyte, nitrite, protein, and/or
	blood. The microscopic examination will be conducted on the
	same urine sample as the abnormal urinalysis test.
Drugs of Abuse:	Amphetamines
8	Barbiturates
	Benzodiazepines
	Cannabinoids
	Cocaine
	Methadone
	Opiates
	Phencyclidine
	Tricyclic antidepressants
	The jene unitaepressums

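### Inclusion 7 requires only females of childbearing potential to be non-lactating, so no written criterion bars a breastfeeding woman who has been sterilised

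*Combined protocol and SAP*

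**What the plan says.** Section 3.3, inclusion 6, admits two classes of women: "Females who participate in this study will be of childbearing or non-childbearing potential". The first class is defined as "Childbearing potential: Physically capable of becoming pregnant". The second consists of post-menopausal and permanently sterile women. Permanent sterility covers removal of both ovaries, removal of the uterus, and "bilateral tubal ligation for at least 6 weeks or documented successful hysteroscopic sterilization".

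Inclusion 7 then states: "Females of childbearing potential must be non-lactating and must have a negative serum pregnancy test at Screening". The synopsis carries the same sentence.

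The supplied text does not mention lactation or breastfeeding anywhere else. Section 3.5 accepts "Surgically sterile" as a single method of contraception. The closest catch-all, exclusion 18 in Section 3.4, covers "Any uncontrolled medical condition that, in the opinion of Medical Monitor or Sponsor, would preclude study participation".

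**The concern.** Inclusion 7 joins two conditions that have different logical scopes. A pregnancy test is relevant to women who can become pregnant, so tying it to childbearing potential makes sense. Being non-lactating is a matter of recent delivery. A woman sterilised at or after a delivery has left the childbearing class but may still be nursing. Attaching both conditions to one class leaves her outside the lactation requirement.

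What is at stake is participant protection, not inference. The protocol itself treats lactation as disqualifying for one class of women and gives no reason for treating the other class differently. Such a woman, if allocated to active drug, would follow the titration to 20 mg, with 35 (± 3) days of exposure before Visit 5 (Section 9.3.8). Her infant is not a trial subject. Section 8.7.1 provides for reporting and follow-up of pregnancy exposure and birth events but has no counterpart for a breastfed infant.

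**Working it through.** No arithmetic applies: the point depends on no rate, effect size or sample size, and the plan states no figure to reproduce. The check is to take one hypothetical candidate through the written rules. She is breastfeeding, had a bilateral tubal ligation more than 6 weeks ago, and meets all criteria unrelated to reproductive status.

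1. **Inclusion 6.** She falls in the permanently sterile branch of the non-childbearing class. Met.
2. **Inclusion 7.** It governs females of childbearing potential only, a term that inclusion 6 has just defined. It does not apply to her.
3. **Inclusion 8 with Section 3.5, Table 1.** Surgical sterility is an accepted single method. Met.
4. **Exclusions 1 to 21 (Section 3.4).** None names lactation. Exclusion 18 needs an uncontrolled medical condition, and exclusion 14 needs an abnormal laboratory value. Lactation triggers neither.
5. **Screening and Baseline procedures (Sections 4.2.10.1 and 4.2.10.2, Appendix A).** Table 2 lists a serum hCG test for females. It detects pregnancy, not lactation. No listed procedure asks about breastfeeding.
6. **Withdrawal (Section 3.6).** Pregnancy is a listed reason for discontinuation. Lactation is not.

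Result: lactation does not stop her at any step, and under Section 3.1 she could be randomized to AMPH ER TAB or matching placebo.

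Repeating steps 1 and 2 for the other sterile branches gives the same answer. On the plain reading of inclusion 6, the 6-week interval qualifies tubal ligation. Removal of the uterus and documented hysteroscopic sterilization carry no stated interval.

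**The case against.** The strongest case on the other side concerns weight. Several things must coincide: a recent delivery, sterilisation at or after it, continued breastfeeding, a Baseline AISRS total of at least 26 with CGI-S of at least 4, and attendance at weekly visits plus a Visit 5 with testing to 14 hours post-dose. Partial safeguards also exist. Screening includes medical history, medication history and a physical examination, and dating a tubal ligation would probably bring a recent delivery to light. Section 3.6 lets the investigator discontinue a subject at discretion or when continuing is not in her best interest. Section 12.4 requires consent to cover possible risks. The consent pages and the Investigator's Brochure are not in the supplied text and may address breastfeeding.

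Much of this stands, and it makes the point minor. It does not close the gap. History-taking may reveal lactation, but no criterion would then exclude her, and discretion may be applied differently across up to 3 sites. Entry is decided by Sections 3.3 and 3.4.

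A reader might also infer more than the text supports:

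- That such a woman meets every entry criterion and will receive amphetamine. She is only not barred by lactation; she must meet all the other criteria, and she may be allocated placebo.
- That the 6-week interval applies to every form of sterilisation. It is attached to tubal ligation.
- That a specific number of the approximately 108 subjects would be affected. The documents give no sex split, postpartum rate or sterilisation rate, so zero is fully compatible with them.
- That harm to an infant is established. The supplied text does not discuss transfer into breast milk. The internal support is that the protocol already treats lactation as disqualifying in the one class it covers.

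**Conclusion.** The gap is real on the wording and minor in size. As written, a breastfeeding sterilised woman who is otherwise eligible is not barred and could be randomized. The number affected is probably very small and cannot be estimated from the documents. Sample size, power, the estimand and every planned analysis are unaffected.

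The conclusion rests on two assumptions: that childbearing potential in inclusion 7 carries the meaning given in inclusion 6, and that no document outside the supplied text imposes a lactation criterion. The documents do not show whether the narrower scope was intended. It may be a drafting slip from combining two conditions in one sentence, which is why the sponsor should either correct it or explain it.

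**What to change.** In Section 3.3, inclusion 7, and in its synopsis copy, split the sentence into two conditions: the existing non-lactating requirement for all females, and the negative serum pregnancy test at Screening for females of childbearing potential. If the sponsor does intend the lactation requirement to depend on childbearing potential, state the reason in Section 3.3 instead.

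The cost is one line in two places. It needs no new test, visit or procedure and no change to the sample size. The downside is that a very small number of otherwise eligible women may be excluded.
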